8.3. Vital Signs

Descriptive summaries of actual values and changes from baseline will be calculated for systolic blood pressure, diastolic blood pressure, heart rate, respiratory rate, BMI, body weight, and oral body temperature. This summary will be presented by treatment group and overall at each visit.

A by-subject listing of all vital sign measurements will be presented.

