13.4.4.4 Vital Signs and Body Weight

Descriptive summaries (mean, SD, median, minimum, and maximum) of actual values and changes from Baseline will be calculated for body weight, body-mass index, systolic blood pressure, diastolic blood pressure, heart rate, and respiratory rate.

The number of subjects with vital signs values categorized as below, within, or above normal ranges, will be tabulated showing change from Baseline (shift tables) for each parameter by treatment group and by study visit. Pre- and post-treatment values may also be presented with an analysis of mean changes from Baseline.

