3.6. Schedule of Events

A detailed schedule of events for the study is provided in [Table 1](#).

Table 1: Schedule of Events

Phase	Screening			Double-blind Treatment						Follow-up	End of Treatment
Period		Washout	Baseline								
Week	-1				1		2		4	5	
Clinic visit	1		2		3		4		5		
Phone visit		1								2	
Study Day	-28 to -14 ^d	-25 to -1 ^d	0	1 to 6	7	8 to 13	14	15 to 27	28	35	
Visit Window (Days)					±2		±2		±2		
Assessments/Procedures											
Informed Consent	X										
Demographics	X										
Medical History	X										
I/E criteria	X		X								
Randomization (IVRS) ^a			X								
Physical Examination	X								X		X
Vital signs ^b	X		X		X		X		X		X
Height	X										
Weight	X		X						X		X
WOMAC Pain ^c	X		X		X		X		X		X
Patient Global Assessment			X		X		X		X		X
Patient Global Impression of Change					X		X		X		X
Pain Intensity 11-Point NRS	X	X	X	X	X	X	X	X	X		X
Dispense Rescue Medication	X		X		X		X				
Use of Rescue Medication ^d		X	X ^d	X	X	X	X	X	X		X
12-lead ECG ^e	X		X						X		X
Clinical Laboratory (Hematology, biochemistry &	X ^d		X						X		X

AD-ST-33.04 Effective date: 30-Jun-2017

urinalysis ⁱ										
Fasting Glucose & Lipids ^g	X		X					X		X
Urine Pregnancy Test	X		X		X		X	X		X
Drug Screen	X		X							
Alcohol Test	X		X							
PK Blood Sample							X	X		X
Subject Diary ^g	X	X	X	X	X	X	X	X		X
Study Medication Application ^h				X ^h	X	X	X	X		
Dermal Evaluations ⁱ			X	X ^k	X	X ^k	X	X ^k	X	X
Prior/Concomitant medications	X	X	X	X	X	X	X	X	X	X
Adverse Events ^j			X	X	X	X	X	X	X	X
X-Ray ^m	X									
Drug Accountability			X ⁿ		X		X	X		X

Abbreviations: AE = adverse event; ET = early termination; ECG = electrocardiogram; ID = identification; I/E = inclusion/exclusion; IVRS = interactive voice response system; NRS = numeric rating scale; PK = pharmacokinetic; WOMAC = Western Ontario and McMaster Universities Arthritis Index.

- a. Subjects will be randomized to HP-5000 [REDACTED], HP-5000 [REDACTED], or placebo in a 1:1:2 ratio.
- b. Vital signs, including heart rate, respiratory rate, and sitting blood pressure will be measured after the subject has been in a supine position for 5 minutes.
- c. WOMAC Pain will include WOMAC pain intensity, WOMAC stiffness, and WOMAC physical function.
- d. Rescue medication may be used during the Washout Period except within 2 calendar days prior to Visit 2 and within 1 day prior to each subsequent visit.

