5.1.5. Analysis Visit Windows

In general, analysis of all variables for this study will use the nominal visit or time point as collected in the CRF/database. Scheduled visits will be selected over unscheduled visits. Unscheduled visits will be presented in data listings. Only dermal evaluation data from unscheduled visits will be included into the summary tables.

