8.6. Pharmacokinetic Analysis

Plasma concentrations of diclofenac (for both HP-5000 [REDACTED] and HP-5000-[REDACTED] will be summarized with descriptive statistics by treatment group.

A by-subject listing of all plasma concentration data will be presented.

9. Changes from Planned Analysis

None

10. Final Database Transfer

After finalization of the analysis, the following will be transferred to the study sponsor:

- Randomization List
- Statistical Analysis Plan
- Data Management Plan
- Annotated CRF
- All SAS code used in the project for statistical analysis, report tables generation, and analysis dataset creation (including all source code for any macros that may be used)
- Tables, listings, and figures as included in the clinical study report
- Final SAS datasets, with full audit trail from initial data entry through final accepted version
- ADaM datasets that are necessary for analysis will be programmed in addition to SDTM (to be modeled in accordance with the Analysis Data Model version 2.1: Implementation Guide version 1.0, and the CDISC Study Data Tabulation Model version 1.4: Implementation Guide version 3.2)
- Define.xml for ADaM and SDTM data sets (to be modeled in accordance with the CDISC Define-XML Specification Version 2.0)
- Study data and analysis data reviewer guides (to be modeled in accordance with the Analysis Data Reviewer's Guide Completion Guidelines Version 1.1, and the Study Data Reviewer's Guide Completion Guidelines Version 1.2) for any unavoidable CDISC checker errors or warnings (found using Pinnacle21)
- Pinnacle21 reports with explanation for errors/warnings if any
- Relevant Correspondence

Database archiving at Premier is performed in accordance with Premier SOPs, which ensure security, integrity, disaster recovery, and adequate backup.

11. References

1. Noven Pharmaceuticals, Inc. protocol number HP-5000-US-05, *A 4-week, Randomized, Double-blind, Multicenter, Placebo-controlled Phase 2 Study to Evaluate the Efficacy and*

AD-ST-33.04 Effective date: 30-Jun-2017

Statistical Analysis Plan,
Sponsor Noven Pharmaceuticals, Inc.
Protocol Number HP-5000-US-05
[REDACTED]

Safety of HP-5000 in Subjects with Osteoarthritis (OA) of the Knee, dated 12-JAN-2018,
Amendment 2

2. [REDACTED]

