14.3.2 Laboratory Safety Data

14.3.2.1.1	SAF	Summary of Change from Baseline for Clinical Chemistry parameters at Week 4
14.3.2.1.2	SAF	Summary of Change from Baseline for Clinical Hematology parameters at Week 4
14.3.2.1.3	SAF	Summary of Change from Baseline for Clinical Urinalysis parameters at Week 4
14.3.2.2.1	SAF	Shift from Baseline to Week 4 for Clinical Chemistry parameters
14.3.2.2.2	SAF	Shift from Baseline to Week 4 for Clinical Hematology parameters
14.3.2.2.3	SAF	Shift from Baseline to Week 4 for Clinical Urinalysis parameters

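### The SAP omits the vital-sign shift table that the protocol requires, without declaring the change, and gives Early Termination laboratory and ECG results no row in its Week 4 tables

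*SAP*

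**What the plan says.** Protocol 13.4.4.4 sets two outputs for vital signs: descriptive summaries, and a categorical table. On the second it says: "The number of subjects with vital signs values categorized as below, within, or above normal ranges, will be tabulated showing change from Baseline (shift tables". The table is to cover every vital sign, broken down by arm and visit. The wording is mandatory. Only the following sentence, on pre- and post-treatment means, is optional.

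SAP 8.3 carries over the first output: "Descriptive summaries of actual values and changes from baseline will be calculated for systolic blood pressure, diastolic blood pressure, heart rate, respiratory rate", together with BMI, weight and temperature. It adds "This summary will be presented by treatment group and overall at each visit" and a by-subject listing. It mentions no normal-range categories and no shift table. SAP section 9, headed "Changes from Planned Analysis", records none.

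For laboratory data, SAP 8.2 keeps low/normal/high shift tables. The planned titles are tied to one visit, for example "Shift from Baseline to Week 4 for Clinical Chemistry parameters". On which visits count, SAP 5.1.5 uses the nominal visit recorded in the database and adds: "Only dermal evaluation data from unscheduled visits will be included into the summary tables".

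**The concern.** Vital signs, laboratory values and ECG are stated safety endpoints (Protocol 13.1.3). For vital signs, a mean change with its minimum and maximum gives the average and one extreme in each direction. It does not say how many subjects in an arm became abnormal, which is what the protocol's table was meant to show. Because section 9 declares no change, a reader of the study report would not learn that a required table had been left out.

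For laboratory and ECG data the issue is who is counted. Subjects who stop early are those in whom a treatment-related abnormality is of most interest. Their last samples are taken at the Early Termination Visit, and the Week 4 tables have no row for that visit.

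**Working it through.** No figure in the plan needs to be reproduced. The check sets the sections side by side.

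**Vital signs**

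| Item | Protocol | SAP |
|---|---|---|
| Descriptive summary | 13.4.4.4: yes | 8.3 and Table 14.3.3.1: yes |
| Shift table by arm and visit | 13.4.4.4: required | 8.3: none; table list 14.3.3: none |
| Listing | not specified in 13.4.4.4 | 8.3: yes |
| Declared change | – | section 9: none |

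The table list under 14.3.3 has one vital-sign table, 14.3.3.1. Its shell repeats Table 14.3.2.1.1, which prints n, mean with 95% CI, SD, median, minimum and maximum. So the protocol requires shift tables and the SAP plans 0. The data exist: vital signs are taken at three scheduled post-baseline visits (Visits 3, 4 and 5) and at Early Termination (Protocol 10.1.3 and 10.1.5). Laboratory values and ECG findings keep shift tables in the SAP; vital signs do not.

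**Laboratory and ECG**

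1. Scheduled post-baseline safety laboratory tests and ECGs occur at Visit 5 (Day 28) only, plus Early Termination (Protocol 10.1.3, 10.1.5 and 17.1). The Week 4 label therefore drops no scheduled on-treatment visit.
2. All six laboratory tables (14.3.2.1.1 to 14.3.2.1.3 and 14.3.2.2.1 to 14.3.2.2.3) are titled for Week 4. The ECG findings tables (14.3.3.3 and 14.3.3.4) show Baseline and Week 4. The ECG parameter table (14.3.3.2) is by study visit.
3. SAP 5.1.5 assigns data by nominal visit and has no rule placing Early Termination results under Week 4. Protocol 8.2.3 has withdrawal data entered on the Early Withdrawal page even when the withdrawal falls at a regular visit, so nothing indicates that those results would carry a Week 4 label.
4. SAP 5.1.5 keeps unscheduled non-dermal results out of summary tables. SAP 5.1.7 sets aside repeat laboratory results unless the first value is missing or invalid.

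From 1 to 4: Week 4 results are tabulated. Early Termination, unscheduled and most repeat results have no stated place in the laboratory or ECG findings tables and may reach only the listings.

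**Related slips in the SAP**

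- The shells for the hematology and urinalysis shift tables (14.3.2.2.2 and 14.3.2.2.3) point to 14.3.2.1.1, the change-from-baseline shell. Programmed literally, they would contain no shift categories. The chemistry shift table has its own correct shell, and the ECG shift table refers to it.
- SAP Table 1, footnote b, reads: "sitting blood pressure will be measured after the subject has been in a supine position for 5 minutes". Protocol 10.2.2.2.1 and footnote b of Protocol 17.1 both describe a supine measurement. The passages need to be reconciled.

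**The case against.** The strongest reply is that little is lost. Safety analysis is descriptive (Protocol 13.4.4), all collected data are listed (SAP 5.1.7), Table 14.3.3.1 prints minimum and maximum, and adverse events are tabulated. All of this stands and lowers the severity. It does not remove the omission of a required table, and a listing or a maximum does not give a count of subjects.

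A reader might go further and infer three things that the documents do not support.

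- *That renal and hepatic abnormalities cannot appear in any safety table.* They can. The chemistry panel includes ALT, AST, BUN and creatinine (Protocol 10.2.2.1.1), and Table 14.3.2.2.1 counts low/normal/high shifts at Week 4.
- *That an abnormal value found at an unscheduled visit and leading to withdrawal would be only in a listing.* Protocol 10.1.5 sends such a visit to the Early Withdrawal procedures and eCRF, so the unscheduled-visit exclusion does not govern those samples. Protocol 11.1.1 says that laboratory abnormalities resulting in withdrawal of treatment should be considered adverse events, which would bring them into Tables 14.3.1.2 and 14.3.1.4. For other laboratory abnormalities, adverse event status is left to the investigator, so this route is only partial.
- *That the blood pressure signal hidden by mean changes can be sized in mmHg.* The documents give no SD of change and no normal ranges, so any such figure would rest wholly on assumption.

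It is also fair to say that the protocol asks for shifts by study visit and does not ask for worst-post-baseline rows or unscheduled data in tables. That part of the fix is a recommendation, not protocol compliance.

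**Conclusion.** The point holds in two parts. First, the SAP leaves out the protocol's vital-sign shift table and says that nothing has changed; this follows directly from the text. Second, Early Termination and unscheduled laboratory and ECG results have no defined place in the laboratory and ECG findings tables. This rests on reading SAP 5.1.5 literally; a programmer might map Early Termination to Week 4, but nothing in the SAP says so.

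The number of subjects affected cannot be derived, because the documents give no early-termination rate. This is a minor SAP–protocol alignment matter that should be put right before unblinding. It does not threaten the safety conclusions, since every value is listed and scheduled Week 4 laboratory shifts are counted.

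**What to change.** 1. Restore the vital-sign shift table, by arm and visit, in SAP 8.3 and 13.1, with a shell. Prespecify the normal ranges, because neither document gives them. If the sponsor prefers to omit the table, declare and justify that in SAP section 9.
2. Add a worst-post-baseline row to the vital-sign, laboratory and ECG shift tables that includes Early Termination and unscheduled results. Amend SAP 5.1.5 to match.
3. Point the hematology and urinalysis shift shells to 14.3.2.2.1.
4. Reconcile SAP Table 1, footnote b, on blood pressure posture with the protocol.

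The cost is SAP wording, a few more shells and the work of defining vital-sign ranges. It needs no new data and changes nothing at the sites.

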8.4. Electrocardiograms

Descriptive summaries will be presented for ECG measures of PR interval, QRS interval, QT interval, QTc interval (both correction methods), and HR. These summaries will be presented by treatment group and overall at each visit.

The frequency and percentage of subjects with normal and abnormal ECG results will be summarized by treatment group and overall at each visit. Shift tables presenting the tabulated number and proportion of subjects with abnormal and normal results post-baseline from baseline category will also be shown in a separate table.

A by-subject listing of all ECG measures and incidence of abnormalities will be presented.

8.5. Dermal Safety

The frequency and percentage of subjects and number of patches with findings related to dermal safety including adhesion, irritation, discomfort, and adhesive residue will be summarized as described below.

8.5.1. Adhesion

Patch adhesion will be evaluated using the following scale:

- 0 = \geq 90% adhered (essentially no lift off of the skin)
- 1 = \geq 75% to < 90% adhered (some lifting off of the skin e.g., edges only)
- 2 = \geq 50% to < 75% adhered (less than half of the system lifting off of the skin)
- 3 = < 50% adhered but not detached (more than half the system lifting off of the skin without falling off)
- 4 = patch detached (patch completely off the skin)

The frequency and percentage of patches in each category will be summarized from the above scale by treatment group and overall at each visit. The number of subjects with the worst score will be summarized and presented. The information from Diary data will be included in summary table and the listing.

8.5.2. Irritation

Irritation will be evaluated using the following scales:

Dermal Response

- 0 = no evidence of irritation
- 1 = minimal erythema, barely perceptible
- 2 = definite erythema, readily visible; minimal edema or minimal papular response
- 3 = erythema and papules
- 4 = definite edema
- 5 = erythema, edema, and papules
- 6 = vesicular eruption
- 7 = strong reaction spreading beyond the application site

Other Effects

- A (0) = slightly glazed appearance
- B (1) = marked glazed appearance
- C (2) = glazing with peeling and cracking
- F (3) = glazing with fissures
- G (3) = film of dried serous exudates covering all or part of the patch site
- H (3) = small petechial erosions and/or scabs
- N (0) = no other observations

The frequency and percentage of subjects with patches in each combined and concatenated category will be summarized from the above scales by treatment group and overall at each visit. The Concatenated Irritation score consists of numerical “Dermal Response” score + the “Other

Effects" lettered score; for example: 2N, 2A, 3G, etc. The Combined irritation score will be calculated as a numerical total; i.e., numerical "Dermal Response" score + numeric equivalent for the "Other Effects" lettered score (note that the "Other Notations" do not have numeric equivalents and do not contribute to the numeric Combined irritation score); for example 2N, 2A, and 3G will be reported as 2, 2, and 6 combined irritations scores respectively.

In addition to the above, the frequency and percentage of subjects with a combined score of 3 or more will be tabulated.

The information from Diary data will be included in the summary table and listings.

8.5.3. Discomfort

Discomfort will be evaluated using the following scale:

- 0 = No discomfort
- 1 = Mild discomfort
- 2 = Moderate but tolerable discomfort
- 3 = Severe, intolerable discomfort
- 4 = Patch not present

The frequency and percentage of subjects with patches in each category will be summarized from the above scale by treatment group and overall at each visit.

The information from Diary data will be included in the summary table and listings.

8.5.4. Adhesive Residue

Adhesive Residue will be evaluated using the following scale:

- 0 = None
- 1 = Light
- 2 = Medium
- 3 = Heavy
- 4 = Patch not present

The frequency and percentage of patches in each category will be summarized from the above scale by treatment group and overall at each visit.

A by-subject listing of individual dermal safety findings will be presented for all dermal safety categories.

8.5.5. Dermal Evaluations at Home

During the Double-blind Treatment Phase at home, subjects will complete a questionnaire about adhesion, skin irritation, discomfort, and adhesive residue in the eDiary. A by-subject listing of this data will be presented in addition to summary tables for each dermal assessment.

Statistical Analysis Plan,
Sponsor Noven Pharmaceuticals, Inc.
Protocol Number HP-5000-US-05
[REDACTED]

8.6. Pharmacokinetic Analysis

Plasma concentrations of diclofenac (for both HP-5000 [REDACTED] and HP-5000-[REDACTED] will be summarized with descriptive statistics by treatment group.

A by-subject listing of all plasma concentration data will be presented.

9. Changes from Planned Analysis

None

10. Final Database Transfer

After finalization of the analysis, the following will be transferred to the study sponsor:

- Randomization List
- Statistical Analysis Plan
- Data Management Plan
- Annotated CRF
- All SAS code used in the project for statistical analysis, report tables generation, and analysis dataset creation (including all source code for any macros that may be used)
- Tables, listings, and figures as included in the clinical study report
- Final SAS datasets, with full audit trail from initial data entry through final accepted version
- ADaM datasets that are necessary for analysis will be programmed in addition to SDTM (to be modeled in accordance with the Analysis Data Model version 2.1: Implementation Guide version 1.0, and the CDISC Study Data Tabulation Model version 1.4: Implementation Guide version 3.2)
- Define.xml for ADaM and SDTM data sets (to be modeled in accordance with the CDISC Define-XML Specification Version 2.0)
- Study data and analysis data reviewer guides (to be modeled in accordance with the Analysis Data Reviewer's Guide Completion Guidelines Version 1.1, and the Study Data Reviewer's Guide Completion Guidelines Version 1.2) for any unavoidable CDISC checker errors or warnings (found using Pinnacle21)
- Pinnacle21 reports with explanation for errors/warnings if any
- Relevant Correspondence

Database archiving at Premier is performed in accordance with Premier SOPs, which ensure security, integrity, disaster recovery, and adequate backup.

11. References

1. Noven Pharmaceuticals, Inc. protocol number HP-5000-US-05, *A 4-week, Randomized, Double-blind, Multicenter, Placebo-controlled Phase 2 Study to Evaluate the Efficacy and*

AD-ST-33.04 Effective date: 30-Jun-2017

Statistical Analysis Plan,
Sponsor Noven Pharmaceuticals, Inc.
Protocol Number HP-5000-US-05
[REDACTED]

Safety of HP-5000 in Subjects with Osteoarthritis (OA) of the Knee, dated 12-JAN-2018,
Amendment 2

2. [REDACTED]

All listings, tables, and graphs will have a header showing the sponsor's company name and protocol, the footer indicates the version of SAS®, the file name, path, and the source of the data (listing number).

General Reporting Conventions:

- All tables and data listings will be developed in landscape orientation.
- Specialized text styles, such as bolding, italics, borders, shading, superscripted and subscripted text will not be used in tables and data listings unless they add significant value to the table, figure, or data listing.
- Only standard keyboard characters should be used in tables and data listings. Special characters, such as nonprintable control characters, printer-specific characters, or font specific characters, will not be used on a table, figure, or data listing. Hexadecimal character representations are allowed (e.g., μ , α , β).
- All titles will be centered on a page. The ICH numbering convention is to be used for all outputs.
- All footnotes will be left justified and at the bottom of a page.
- Missing values for both numeric and character variables will be presented as blanks in a table or data listing. A value of zero may be used if appropriate to identify when the frequency of a variable is not observed.
- All date values will be presented as ddmmmyyyy (e.g., 29AUG2011) format. A 4-digit year is preferred for all dates.
- If applicable, all observed time values will be presented by using a 24-hour clock HH:MM:SS format (e.g., 01:35:45 or 11:26). Seconds should only be reported if they were measured as part of the study.
- All tables and data listings will have the name of the program, the location, and a run date and time stamp on the bottom of each output.

Population Summary Conventions

- Population sizes may be presented for each classification factor as totals in the column header as (N=xxxx), where appropriate.
- Population sizes shown with summary statistics are the sample size (n) of subjects with non-missing values.
- All population summaries for categorical variables will include all categories that were planned and for which the subjects may have had a response. Percentages corresponding to null categories (cells) will be suppressed, however counts and percentages of missing

values may be needed.

- All population summaries for continuous variables will include: N, mean, median, SD, minimum, and maximum. Other summaries (e.g., number missing, geometric mean, quartiles, 95% CIs) may be used as appropriate.
- All percentages are rounded and reported to a single decimal point (xx.x %). A percentage of 100% will be reported as 100%. No value of 0% will be reported. Any computation of percent that results in 0% is to be presented as a blank.

